9.2.3. Safety Evaluations

Any clinically relevant changes occurring must be recorded on the eCRF. Any clinically significant abnormalities, including those persisting at the end of the study/early withdrawal, will be followed by the investigator until resolution or until a clinically stable endpoint is reached.

The study will include the following evaluations of safety and reactogenicity according to the timepoints provided in the [Time and Events Schedule](#).

Adverse Events

All AEs will be reported as specified in Section [12.3.1](#), All Adverse Events.

Unsolicited AEs

Unsolicited AEs will be reported by the subject (ie, by a caregiver, surrogate, or the subject's legally acceptable representative) from the time of each vaccination through the following 28 days, or early discontinuation. Relatedness of unsolicited AEs should be determined by the investigator. Additionally, AEs that are related to the study procedures or are related to non-investigational (concomitant) Janssen products will be reported from ICF signature onwards.

Solicited AEs

Information related to solicited AEs as defined in Section [12.1.1](#), will be recorded by the subject's parent/legal guardian or caregiver in a diary for 7 days after each vaccination. Each subject's parent/legal guardian or caregiver will be provided with a diary and instructions on how to complete the diary (Section [9.1.1](#)). There will be a minimum 30-minute (or 60-minute, depending on local or study-site requirements) post-vaccination assessment of solicited events at the site. Diary information will be transcribed by the study personnel in the appropriate eCRF pages.

Injection Site (Local) Adverse Events

Each subject's parent/legal guardian or caregiver will be asked to note in the diary occurrences of pain/tenderness, erythema and induration/swelling at the study vaccine injection site daily for 7 days post-vaccination. The extent (largest diameter) of any erythema, and induration/swelling should be measured (using the ruler supplied) and recorded daily. Induration/swelling should also be graded using the functional scale.

- **Injection Site Pain/Tenderness**

Injection site pain (eg, stinging, burning) is an unpleasant sensory and emotional experience associated with actual or potential tissue damage and occurring at the immunization site (with or without involvement of surrounding tissue). Injection site tenderness is a painful sensation localized at the injection site upon palpation and/or movement of the limb. Due to subjective nature of the reaction, the severity assessment of pain/tenderness is self-reported (if a subject is unable to provide self-report, other reporters include parent/care giver or healthcare provider).¹⁴

- **Injection Site Erythema**

Injection site erythema is a redness of the skin caused by dilatation and congestion of the capillaries localized at the injection site. It can best be described by looking and measuring.

- **Injection Site Swelling/Induration**

Injection site swelling is a visible enlargement of an injected limb. It may be either soft (typically) or firm (less typical). Injection site induration is a palpable thickening, firmness, or hardening of soft tissue, usually has well-demarcated palpable borders, can be visible (raised or sunken compared to surrounding skin), is often 'woody' to touch and has a flat shape. As differentiation between swelling and induration may be difficult without healthcare professional's assessment, both symptoms have been combined to allow self-assessment by the subject's parent/legal guardian or caregiver. Both swelling and induration can best be described by looking and measuring.

Note: Any other injection site events not meeting the above case definitions should be reported separately as unsolicited AEs.^{28,29}

Systemic Adverse Events

The subject's parent/legal guardian or caregiver will be instructed on how to record daily temperature^{aa} using a thermometer provided for home use. The subject's parent/legal guardian or caregiver should record the temperature in the diary in the evening of the day of vaccination, and then daily for the next 7 days approximately at the same time each day^{bb}. If more than one measurement is made on any given day, the highest temperature of that day will be used in the eCRF.

Fever is defined as endogenous elevation of body temperature ≥ 38.0 °C, as recorded in at least one measurement.³²

The subject's parent/legal guardian or caregiver s will also be instructed on how to note daily in the diary for 7 days post-vaccination symptoms of the following events: loss of appetite, vomiting, diarrhea, decreased activity/lethargy, irritability/crying and fever (ie, body temperature ≥ 38.0 °C).

The severity of these solicited systemic AEs will be graded by the investigator according to the criteria presented in Section 12.1.3, Severity Criteria.

If a solicited local or systemic AE is not resolved by 7 days post-vaccination, the follow-up will be captured on the diary. The subject's parent/legal guardian or caregiver will be instructed to record the date of last symptoms and maximum severity in the diary after resolution.

^{aa} Recommended to be measured axillary (actual routes to be recorded in the eCRF).

^{bb} All Day 8 post-vaccination diary assessments, including temperature measurements, may be collected earlier to coincide with the corresponding clinic visit.

9.2.3.1. Vital Signs

Pulse/heart rate measurements should be preceded by at least 5 minutes of rest in a quiet setting without distractions (eg, television, cell phones):

- Heart rate (beats per minutes), and respiratory rate (breaths per minute)
- Body temperature (the axillary route is recommended)
- Oxygen saturation (SpO₂)

Confirmatory vital signs measurement can be performed if inconsistent with a prior measurement. If any clinically significant changes in vital signs are noted, they will be reported as AEs and followed to resolution, or until reaching a clinically stable endpoint.

9.2.3.2. Physical Examination

Full physical examination, including length and weight, will be carried out at screening. At all other visits, abbreviated, symptom-directed examinations will be performed by the investigator based on clinically relevant issues, clinically relevant symptoms and medical history. Symptom-directed physical examination may be repeated if deemed necessary by the investigator.

Physical examinations will be performed by the investigator or an appropriately trained delegate. Any clinically relevant abnormalities or changes in severity observed during the review of body systems should be documented in the eCRF.

9.2.4. Other Evaluations

At Visit 12 (6 months post-Dose 3), parents/legal guardians or caregivers (where allowed by local regulations) of each study subject will be invited to complete an IEC/IRB approved Participant Experience Survey, to share to their experience in this study. The responses will be collected by an external party and anonymously provided to the sponsor.

10. SUBJECT COMPLETION/DISCONTINUATION OF STUDY VACCINE/ WITHDRAWAL FROM THE STUDY

10.1. Completion

A subject will be considered to have completed study vaccination if he or she has received all three study vaccinations. A subject will be considered to have completed the study if he or she has completed assessments through to the end of the study (see Section [17.9.1](#)).

10.2. Discontinuation of Study Vaccine/Withdrawal from the Study

Discontinuation of Study Vaccine

A subject will not be automatically withdrawn from the study if he or she has to discontinue from study vaccination before the end of the study vaccine regimen.

Subjects will be discontinued from study vaccination for the reasons listed below. These subjects must not receive any additional dose of study vaccine but should continue other study procedures, eg, safety follow-up:

- Anaphylactic reaction following vaccination, not attributable to causes other than vaccination
- Any related SAE
- Any related AE, worsening of health status or intercurrent illness that, in the opinion of the investigator, requires study vaccine discontinuation
- Repeated failure to comply with protocol requirements
- Decision by the sponsor, investigator, local regulatory authorities or IRB/IEC

Note: A subject will not be automatically withdrawn from the study if consent is withdrawn only for blood draws; they may remain in the study and continue to receive study vaccine and undergo safety follow-up.

Withdrawal From the Study

Parents/legal guardians have the right to withdraw their child from the study at any time for any reason without affecting the right to treatment by the investigator. Although parents/legal guardians are not obliged to give a reason for withdrawing prematurely, the investigator should make a reasonable effort to ascertain the reason(s) while fully respecting the subject's rights.

A subject will be withdrawn from the study for any of the following reasons:

- Lost to follow-up
- Withdrawal of consent
- Death

Any unnecessary study discontinuation should be avoided. Should a subject be withdrawn, all efforts should be made to complete and report the observations as thoroughly as possible. Whenever a subject is withdrawn from the study, independent of the reason, a final evaluation should be completed for that subject and the major reason for which the subject was withdrawn must be stated. If a subject is lost to follow-up, every reasonable effort must be made by the study-site personnel to contact the subject and determine the reason for discontinuation/withdrawal. The measures taken to follow-up must be documented.

When a subject is withdrawn before completing the study, the reason for withdrawal is to be documented in the eCRF and in the source document. Study vaccine assigned to the withdrawn subject may not be assigned to another subject. In general, subjects who withdraw will not be replaced, unless the subject was randomized but did not receive any study vaccine. However, any randomized subject withdrawn from the study for reasons other than due to an AE after the first dose but before the second dose might be replaced at the discretion of the sponsor.

If a subject withdraws early from the study, assessments for early withdrawal should be obtained (see Section 9.1.3.2.4).

Subjects who wish to withdraw consent from participation in the study will be offered a single exit visit for safety follow-up (prior to formal withdrawal of consent). They have the right to refuse.

Withdrawal From the Use of Samples in Future Research

The subject may withdraw consent for use of samples for future research (see Section 16.2.5). In such a case, samples will be destroyed after they are no longer needed for the clinical study. Details of the sample retention for research are presented in the main ICF.

10.3. Contraindications to Vaccination

The following events constitute a contraindication to vaccination at that point in time:

- Severe acute illness at the time of vaccination. This does not include minor illnesses such as diarrhea.
- Fever (body temperature ≥ 38.0 °C) at the time of vaccination.

If any of these events occur at the scheduled time for the first vaccination, enrollment at a later date is permitted^{cc} at the discretion of the investigator and after consultation with the sponsor. If any of these events occur at the scheduled time for the second or third vaccination, the subject may be vaccinated up to 10 days beyond the scheduled vaccination, or be withdrawn from further vaccination at the discretion of the investigator and after consultation with the sponsor. In the event of an ongoing AE or other situation precluding subject vaccination within 10 days, subjects may be vaccinated beyond the 10-day window at the discretion of the sponsor.

Note: Medically-indicated vaccines should be given at least 14 days before or 14 days after study vaccine administration. If a vaccine is indicated in a post-exposure setting (eg, rabies or tetanus), it must take priority over the study vaccine (see Section 4.3).

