- b. End of first RSV season after the first dose. Note: Subjects' parents/legal guardians will be informed of the timing of the start and end of the RSV season in accordance with the country/region-specific RSV local surveillance system (if available) or the local surveillance at the site (standard of care assessments, if available).
- c. For those subjects who are unable to continue participation in the study up to the visit at the end of the RSV season, but for whom consent is not withdrawn, an exit visit will be conducted as soon as possible.
- d. If any subject comes in earlier than Day 8 for Visit 4 or Day 36 for Visit 7 (allowed windows are $-1/+3$ and ± 2 days, respectively), a subsequent phone call will be made at the end of the diary period to collect diary card information recorded between the actual visit and the end of the diary period on Day 8 (or Day 36).
- e. The timings of visits after the second/third vaccinations will be determined relative to the actual day of that vaccination.
- f. If any subject comes in earlier than Day 64 for Visit 10 (allowed window is ± 2 days), a subsequent phone call will be made at the end of the diary period to collect diary card information recorded between the actual visit and the end of the diary period on Day 64.
- g. Signing of the ICF should be done before any study-related activity.
- h. Respiratory rate, heart rate, body temperature, oxygen saturation (SpO₂). Note that body temperatures are recommended to be measured axillary (actual routes to be recorded in the eCRF).
- i. 0.5 mL of blood for serostatus assessment can be collected at screening by venous blood sample or fingerstick, at the discretion of the investigator. If 0.5 mL is collected at screening, baseline blood draw for immunogenicity should be on Day 1.
- j. Note: serostatus may be assessed via the RSV EIA if available from a different study of the sponsor (VAC18194RSV2001). If done within 42 days of first dose, this assessment would not have to be repeated in the absence of a history of respiratory infection during that period.
- k. To include exclusion criteria 1, 2, 3, 4, 6, 7, 9, 10, 11, 13, 14, 15, 16, 17, and 18.
- l. Blood for cellular immunity will also provide plasma for humoral assessments.

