- m. Investigator must check for acute illness or body temperature ≥ 38.0 °C at the time of vaccination. If before the first vaccination, the subject may be enrolled at a later date if within the screening window (otherwise, rescreening is required), or be withdrawn at the discretion of the investigator and after consultation with the sponsor. If before the second or third vaccination, the subject may be vaccinated up to, and no later than 10 days after the scheduled vaccination, or be withdrawn at the discretion of the investigator and after consultation with the sponsor. In the event of an ongoing AE or other situation precluding subject vaccination within 10 days, subjects may be vaccinated beyond the 10-day window at the discretion of the sponsor.
- n. PBMC samples to assess cellular immune responses will be collected at sites that have the capability to process the cells within the time frame specified in the laboratory manual.
- o. Subjects will be closely observed for a minimum of 30 minutes (or 60 minutes, depending on local or study-site requirements) post-vaccination. Any unsolicited, solicited local and systemic AEs, and vital signs will be documented by study-site personnel following this observation period.
- p. All AEs and special reporting situations related to study procedures or to non-investigational (concomitant) Janssen products will be reported from ICF signature onwards. All other AEs (unsolicited) and special reporting situations will be reported from each vaccination through the following 28 days.
- q. Concomitant medications will be collected from the time of each vaccination, through 28 days after each vaccination, and additionally outside of these periods when associated with any SAE, RTI or OM case. Pre-study therapies administered up to 30 days before first dose of study vaccine will be recorded during screening.
- r. Collection of any concomitant medication given in response to an RTI or OM case.

- s. All SAEs related to study procedures or to non-investigational (concomitant) Janssen products will be reported from ICF signature onwards. All other SAEs will be reported from the first vaccination onwards.
- t. Any RTI or otitis media case fulfilling the criteria of an SAE will be reported as such during the entire study period.

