 - For all subjects, there are pre-specified rules that would result in pausing of further study vaccinations if predefined conditions occur, preventing exposure of new subjects to study vaccine until the PI(s) or designee/SRP/S and IDMC reviews all safety data (see Section 11.10).
 - Subjects will discontinue study vaccine for the reasons included in Section 10.2.
 - If acute illness (excluding minor illnesses such as diarrhea) or fever (body temperature $\geq 38.0^{\circ}\text{C}$) occur at the scheduled time for the first vaccination, the subject may be enrolled at a later date^f, or be withdrawn at the discretion of the investigator and after consultation with the sponsor.
 - If acute illness (excluding minor illnesses such as diarrhea) or fever (body temperature $\geq 38.0^{\circ}\text{C}$) occur at the scheduled time for the second or third vaccination, the subject may be vaccinated up to 10 days beyond the scheduled vaccination, or be withdrawn from further vaccination at the discretion of the investigator and after consultation with the sponsor. In the event of an ongoing AE or other situation precluding subject vaccination within 10 days, subjects may be vaccinated beyond the 10-day window at the discretion of the sponsor.
 - Contraindications to vaccination are included in Section 10.3.
 - During the RSV season, careful monitoring will be in place to check for the occurrence of RTI/otitis media^s. The subject's parent/legal guardian or caregiver will record any signs and symptoms of RTI (eg, runny nose, fever, severe cough, wheezing, rapid breathing, or difficulty breathing) on a daily basis using the study-specific RTI Symptoms Form, starting on the first day their child experiences symptoms, including the day on which symptoms resolve. Nasal samples will be collected by the site staff and analyzed for identification and confirmation of RSV infection. The presence of severe LRTI and RSV infection will be determined by the CEC. The IDMC will be informed of any case of severe RSV-LRTI as assessed by the CEC. For such cases, a monitoring rule is applied (see Section 11.3.1.3).

^f If within the screening window. Otherwise, rescreening is required.

^s *Note:* The RTI procedures (see Section 9.2.2) also apply to all otitis media cases.

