4.2. Exclusion Criteria

Any potential subject who meets any of the following criteria will be excluded from participating in the study:

1. Criterion amended per Amendment 4:
 - 1.1 Subject has moderate or severe illness (this does not include minor illnesses such as diarrhea) or temperature ≥ 38.0 °C within 24 hours prior to the first dose of study vaccine; the subject may be enrolled at a later date[†], or be withdrawn at the discretion of the investigator and after consultation with the sponsor.
2. Any subject who has had an RTI between screening and randomization that the PI(s) feels would make them ineligible.
3. Subject's weight is below 10th percentile according to World Health Organization (WHO) pediatric growth and weight charts.⁷
4. Subject has any clinically significant acute or chronic medical condition (eg, history of seizure disorders, bleeding/clotting disorder, autoimmune disease, active malignancy, systemic infections, congenital heart disease, history of any pulmonary condition requiring medication, atopy, reactive airway disease, medically-confirmed wheezing, bronchoconstriction or treatment with a $\beta 2$ agonist, cystic fibrosis, bronchopulmonary dysplasia, chronic pulmonary disease, medically-confirmed apnea, hospitalization for respiratory illness, or mechanical ventilation for respiratory illness) that, in the opinion of

[†] If within the screening window. Otherwise, rescreening is required.

the investigator, would preclude participation.

5. Subject has major congenital anomalies (after discussion with the SRP/S) or known cytogenetic disorders (eg, Down's syndrome).
6. Subject has had major surgery within the 4 weeks prior to randomization or has planned major surgery through the course of the study.
7. Subject is in receipt of, or planning to receive, live attenuated vaccine (eg, measles, mumps and rubella [MMR] or varicella, but excluding rotavirus vaccine) within 28 days of each study vaccination (ie, before and after); other vaccines (eg, influenza, pertussis, polio or rotavirus) should be given at least 14 days before or 14 days after each study vaccination.

Note: Planning for routine childhood vaccinations will be available from the site to ensure that these can be taken at appropriate times during the study.

8. Subject has known or suspected immunodeficiency, such as known HIV infection.

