After verification of selected eligibility criteria,^a abbreviated physical examination (at the discretion of the investigator) and measurement of vital signs, length and weight will be performed for all subjects pre-vaccination. Before the second or third vaccination, the investigator must check for any symptoms of an acute illness. In such a situation, the subject may be vaccinated up to, and no later than 10 days after the scheduled vaccination, or be withdrawn at

^x Exclusion criterion 1, 2, 3, 4, 6, 7, 9, 10, 11, 13, 14, 15, 16, 17, and 18.

^y If within the screening window. Otherwise, rescreening is required.

the discretion of the investigator and after consultation with the sponsor. In the event of an ongoing AE or other situation precluding subject vaccination within 10 days, subjects may be vaccinated beyond the 10-day window at the discretion of the sponsor.

Administration of study vaccine.

Subjects will be closely observed for a minimum of 30 minutes (or 60 minutes, depending on local or study-site requirements) post-vaccination to monitor for the development of any acute reactions, or longer if deemed necessary by the investigator. Any unsolicited, solicited local or solicited systemic AEs and vital signs will be documented in the eCRF by study-site personnel following this observation period.

A subject diary, thermometer, and ruler will be provided to measure and record body temperature and solicited local and systemic AEs for 7 days post-vaccination.

RTI Symptoms Forms will be distributed to each subject's parent/legal guardian or caregiver.

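### For doses 2 and 3 the protocol states three non-equivalent illness conditions, so an afebrile, moderately ill child can be dosed under one section and deferred or withdrawn under another

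*Protocol*

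**What the plan says.** Four places in the protocol tell a site what to do when a child is ill at the dose 2 or dose 3 visit.

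- Section 10.3 lists two contraindications: fever, and "Severe acute illness at the time of vaccination. This does not include minor illnesses such as diarrhea".
- Section 3.3.5 begins "If acute illness (excluding minor illnesses such as diarrhea) or fever" and continues that, if these "occur at the scheduled time for the second or third vaccination, the subject may be vaccinated up to 10 days beyond the scheduled vaccination". No severity grade is given.
- Section 9.1.3.2.1, for Visits 5 and 8, says "Before the second or third vaccination, the investigator must check for any symptoms of an acute illness". It then offers the same 10-day delay or withdrawal.
- Footnote m of the Time and Events Schedule asks for a check for acute illness or a temperature of 38.0 °C or more, with no exception for minor illness. The child may then be dosed late, "or be withdrawn at the discretion of the investigator and after consultation with the sponsor".

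A fifth wording enters through footnote k, attached to the row for verifying eligibility and contraindications, which is marked pre-dose at all three vaccination visits: "To include exclusion criteria 1, 2, 3, 4, 6, 7, 9, 10, 11, 13, 14, 15, 16, 17, and 18". Criterion 1 in Section 4.2 reads "Subject has moderate or severe illness (this does not include minor illnesses such as diarrhea) or temperature" of at least 38.0 °C, but it is tied to the 24 hours before the first dose.

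On what follows, Sections 3.3.5 and 10.3 speak of stopping further vaccination, while footnote m and Section 9.1.3.2.1 speak of withdrawal without qualification. Section 10.2 says of children whose vaccination is discontinued: "These subjects must not receive any additional dose of study vaccine but should continue other study procedures, eg, safety follow-up".

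**The concern.** These rules decide which children are dosed while ill, which are dosed late and which may miss a dose. If the passages set different thresholds, two sites can treat the same child differently and both can point to the protocol.

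This touches the data in three ways. The solicited systemic events in Section 9.2.3 (fever, vomiting, diarrhea, loss of appetite, lethargy, irritability) belong to the primary endpoint and are also symptoms of ordinary toddler illness, so dosing more or fewer ill children changes the background rate. A dose given to a moderately ill child is a deviation under one passage and compliant under another, so deviations cannot be classified consistently. And where a dose is missed, Section 11.1 removes later samples from the per-protocol immunogenicity set.

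**Working it through.** The plan gives no figure to reproduce here. The check is a side-by-side reading of each passage that applies to doses 2 and 3.

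| Passage | Illness that triggers action | Minor illness excepted? | Fever named? | Outcome if not delayed |
|---|---|---|---|---|
| Section 10.3 | Severe acute illness | Yes | Yes | Off further vaccination |
| Section 3.3.5 | Acute illness, no grade | Yes | Yes | Off further vaccination |
| Section 9.1.3.2.1, Visits 5 and 8 | Any symptoms of acute illness | No | Not in that sentence | Withdrawn, unqualified |
| Footnote m | Acute illness, no grade | No | Yes | Withdrawn, unqualified |

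All four allow a delay of up to 10 days, and longer at the sponsor's discretion. Criterion 1.1 is left out because its own text concerns the first dose.

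Four children at Visit 5 or 8, taken through each passage:

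| Child | 10.3 | 3.3.5 | 9.1.3.2.1 | Footnote m |
|---|---|---|---|---|
| Afebrile, minor illness | No action | No action | Action | Action |
| Afebrile, moderate acute illness | No action | Action | Action | Action |
| Afebrile, severe acute illness | Action | Action | Action | Action |
| Fever only | Action | Action | Not named | Action |

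1. The illness conditions in 10.3, 3.3.5 and 9.1.3.2.1 are pairwise different. Footnote m shares the 9.1.3.2.1 position on minor illness and adds fever. The count of three does not need criterion 1.1.
2. The clearest conflict is the moderately ill child without fever, for whom 10.3 stands alone against the other three. The minor-illness row also splits, but less firmly, because footnote m and 9.1.3.2.1 are short procedural instructions that may simply have omitted the exception.
3. Taking the strictest passage does not settle the matter. It would cancel the minor-illness exception that 10.3 and 3.3.5 state expressly. Section 3.3.5 also refers the reader to 10.3 for contraindications while giving a different condition itself.
4. Section 10.3 is unclear on its own terms: an exception for minor illness adds nothing to a rule already confined to severe illness. The reader cannot tell whether the severity word was meant as a threshold.
5. Footnote k asks sites to re-check criterion 1 at doses 2 and 3, although its wording does not literally apply there and it uses yet another threshold (moderate or severe).
6. On outcome, footnote m uses the same withdrawal phrase for a child not yet dosed, who would leave the study, and for a child already dosed, whom Sections 9.1.3.3 and 10.2 keep in follow-up.

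Scale: 36 planned children × 2 = 72 dose 2 and dose 3 visits, and 1/18 = 5.6% of an arm per child. The share of visits at which a child is mildly or moderately ill is not in the documents, so no count of affected visits is offered. The textual conflict does not depend on it.

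**The case against.** The best reply is that the procedural passages only tell the investigator to check and then say the child may be dosed later. Nothing orders a site to defer a runny nose, and 10.3 is the one section that defines contraindications. That stands in part. It weakens the minor-illness conflict, and it means sites can, rather than will, diverge. It does not remove the moderate-illness conflict, because 3.3.5 and 10.3 differ in substance.

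A reader might also infer several stronger things that the documents do not support.

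- *That 10.3 admits to dose 1 a child whom criterion 1.1 excludes, such as one febrile the evening before.* Eligibility and contraindications are cumulative: the Schedule row verifies both, and Section 4 forbids waivers and excludes a child who ceases to qualify before the first dose.
- *That criterion 1.1 bars a moderately ill child from dose 2.* Its wording is limited to the first dose. Footnote k creates confusion, not a clear bar.
- *That fever is overlooked at Visits 5 and 8.* Vital signs, including temperature, are taken before dosing, and footnote m, 3.3.5 and 10.3 all name the fever threshold.
- *That a dosed child could lose the two-season follow-up for enhanced disease.* Section 9.1.3.3 includes every child who received a dose. Section 10.2 lists only loss to follow-up, withdrawn consent and death as reasons for leaving the study.
- *That illness symptoms could not be separated from vaccine effect.* Allocation is 1:1 and observer-blind with a concurrent control, so inconsistent handling should fall on both arms alike.
- *That the per-protocol set would shrink materially.* A delayed dose is not a missed dose, and delay is the more likely outcome.

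Finally, 37 children were already enrolled at Amendment 6, so many of these visits may be past. The documents do not say how many remained.

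**Conclusion.** The inconsistency is real and lies in the current text. For doses 2 and 3 there are three non-equivalent illness conditions with no order of precedence, a re-verification instruction pointing at a first-dose criterion, and two descriptions of withdrawal. The clearest consequence is for the afebrile child with a moderate illness, who can be dosed under Section 10.3 and deferred or withdrawn under the other passages.

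Its weight is modest. The expected effect is inconsistent dosing of ill children, inconsistent deviation classification and some added noise in solicited events, where one child moves an 18-child arm by 5.6 percentage points. There is no reason to expect directional bias. This rests on two assumptions: that the blind holds at the point where dosing is decided, and that investigators normally use the delay rather than drop the dose. Any doses already given would still need one definition so that deviations are judged alike.

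**What to change.** Reconcile footnotes k and m of the Time and Events Schedule, Section 3.3.5, criterion 1.1 in Section 4.2, Section 9.1.3.2.1 and Section 10.3 to a single definition of illness at the time of dosing. It should cover severity, the treatment of minor illness and the temperature condition, and be stated separately for dose 1 and for doses 2 and 3 if they are meant to differ. The other passages should then refer to it and not restate it. Footnote k should say what re-checking criterion 1 means after the first dose.

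Align the withdrawal wording in footnote m and Section 9.1.3.2.1 with Sections 9.1.3.3 and 10.2, so that it is plain whether a dosed child stays in safety follow-up.

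Which threshold applies is for the sponsor's clinical team; this review takes no position. The cost is a clarifying amendment and a note to sites, with no new procedures or data collection.
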